Study Endpoints	
Primary Endpoint: Number of VRP-Clinic neck movements that the evaluator recognizes as useful for rehabilitation. Success acceptance criteria defined as: 80%
 
Secondary Endpoint: Safety – Record of any adverse event occurring during the study. All AEs will be recorded and evaluated as part of the risk management for the device

	Study Protocol			
	VRP-CLINIC SOFTWARE EVALUATION - IN SUPPORT OF REHABILITATION			
Protocol#	VRP02	Version #, Date.	Version 01 22-March-2017	Page 6 of 12

INTRODUCTION

One of the most common musculoskeletal dysfunctions in the population is dysfunction of the cervical spine reaching an annual prevalence of 30-50% in western societies and associated with considerable pain, disability, and costs [1, 2].

Physical therapies are first line treatments aimed at improving muscle strength and range of motion, often requiring considerable commitment by subjects over a long period of time [3] and frequently requiring a home exercise program for a successful outcome [4]. However, compliance to home exercises is not as high as desired therefore, it is imperative to include new motivational interventions to increase compliance.

Virtual reality (VR) technology has been used for several decades for a variety of psychosocial interventions. The use of VR was studied for a variety of rehabilitation conditions [5, 6]. Specifically, the effect of neck exercises using VR was previously tested on both asymptomatic individuals and patients with chronic neck pain and was shown to be useful in increasing cervical motion [7-9].

STUDY RATIONAL

In recent years, commercial and research groups have been studying the effect of VR systems on the rehabilitative progress and developing new platforms. As the variety of available products widens, each system focuses on specific hardware and different rehabilitation aspects. The software presented in the current study focuses on the rehabilitation of the upper body.

STUDY OBJECTIVES

The current study was designed to evaluate neck movements performed according to the VRP-Clinic software, and to verify that they promote physical activities that correspond with physical rehabilitation.

STUDY DEVICE

Indications for Use

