VRHealth's VRP-Clinic software, coupled with compatible VR (virtual reality) hardware (headset and supporting PC) is intended to promote physical rehabilitative processes of individuals requiring training of their head and neck muscles/joints as part of a physical therapy session.

Prior to the first session using VRP-clinic, a medical practitioner will assess the patient and will determine the selection of movements included in such training.

Device Description

VRP-clinic Software

VRP-Clinic software is used with several supported hardware platforms, delivering the same experience in each. Currently, the VRP-Clinic software supports Oculus rift and HTC VIVE

 
המרכז הרפואי שערי צדק ירושלים
	Study Protocol			
	VRP-CLINIC SOFTWARE EVALUATION - IN SUPPORT OF REHABILITATION			
Protocol#	VRP02	Version #, Date.	Version 01 22-March-2017	Page 7 of 12

platforms – both systems use a PC based virtual reality platform and infra-red sensors to detect head movement of the user.

A description of the software algorithm, a major routine/function level flow chart, a signed validation document, and a risk analysis table can be found in the Investigator Brochure.

Hardware platform

VRP-Clinic software is used with several supported hardware platforms, delivering the same experience in each. Currently, the VRP-Clinic software supports Oculus rift and HTC VIVE platforms – both systems uses a PC based virtual reality platforms and used infra-red sensors to detect head movement of the user. In the current study, the Oculus rift platform will be used. A description of the Oculus rift device and the manufacturer details can be found in Investigator Brochure.

STUDY DESIGN

Overview

Single center, prospective, open label, single arm.

The study will take place at Shaare Zedek Medical Center (SZMC). The study will include a single visit. Twenty (n=20) healthy subjects will be recruited to this study. Subjects must meet the eligibility criteria detailed in the protocol and sign the informed consent form prior to any study procedure.

Each subject will receive an explanation from the study team on the device and study procedures. Medical and demographic information will be collected.

The subject will put on the VR headset and perform a series of neck movements guided by graphic instructions appearing in the VR environment. The study team will record any adverse event (AE) if such happens during/post training.

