The session will be recorded with a video camera. Camera recording will start after the VR headset is placed on the subjects' head and terminate before removing it, to ensure the participants' privacy.

The video will be viewed and evaluated separately by 4 clinicians. The clinicians will identify each movement seen on the video from a predefined list and determine if such a movement is recommended as part of a rehabilitation training program for neck related pathologies.

Endpoints:

Primary Endpoint

Number of VRP-Clinic neck movements that the assessing clinician recognizes as rehabilitation movements.

Success acceptance criteria defined as: 80%

Secondary Endpoint:

Safety – Record of any adverse event occurring during the study.

All AE's will be recorded and evaluated as part of the risk management for the device

Study Duration

	Study Protocol			
	VRP-CLINIC SOFTWARE EVALUATION - IN SUPPORT OF REHABILITATION			
Protocol#	VRP02	Version #, Date.	Version 01 22-March-2017	Page 8 of 12

Duration of subject's participation: 30 minutes of which the actual exercise is expected to take not more than 5 minutes

Study duration: The total study duration from recruitment to final data collection is estimated to be four months

STUDY POPULATION AND SUBJECT SELECTION

Source and sample size

Twenty (n=20) healthy adult subjects will be included in this study. The subject will be recruited by the investigator by use of an IRB approved advertisement.

Eligibility

Each subject will be evaluated by the Investigator to assess his/ her suitability for entry into this study according to the following criteria:

Inclusion Criteria

Eligible subjects must meet all of the following inclusion criteria:

1. Healthy male or female
2. Age 18-65

Exclusion Criteria

Eligible subjects must not meet any of the following exclusion criteria:

1. History of neck related disorders (Whiplash, disc degeneration disease or other acute cervical spine conditions)
2. Current neck pain
3. Under medical treatment or observation for any health-related issue during the study
4. Recent trauma
5. Oncology background
6. Acute disease/illness
7. Pregnancy.
8. Using drugs that could potentially affect physical function and balance (such as corticosteroids, antipsychotics or antidepressants)
9. Vision problems that require glasses (not all frame types can fit into the headset)

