The investigator may withdraw a subject if, in his clinical judgment, it is in the best interest of the subject or if the subject cannot comply with the protocol. At the discretion of the investigator, these subjects may be replaced. Attempt should be made to complete any examinations.

Subject Termination

In case of dropout or subject removal the investigator will describe the reason for discontinuing the subject's participation in the Termination CRF.

Compensation

At the end of the session, subjects will receive a coupon for use at the local cafeteria for purchase of a hot drink and cake ("café u maafe") approximately worth 15 NIS as compensation for their time.

	Study Protocol			
	VRP-CLINIC SOFTWARE EVALUATION - IN SUPPORT OF REHABILITATION			
Protocol#	VRP02	Version #, Date.	Version 01 22-March-2017	Page 9 of 12

STUDY PROCEDURES

Screening

Eligibility: the volunteer will be screened to determine if he/she meets the study inclusion/exclusion criteria.

Informed consent Prior to the study visit, informed consent will be obtained. When the participant fully understands the procedure, possible benefits and risks of the study, the subject will be asked to sign and date the informed consent document.

Subject number If the subject meets the study inclusion/exclusion criteria, the subject will be assigned the next consecutive number.

Medical history and demographic information: Basic medical and demographic information will be collected including age, gender, height, weight, head circumference, general medical background and specific information related to head/neck.

Interventions and procedures:

Subject Preparation and Instructions

The subject will sit on a steady chair, with back support, in front of a desk where the device sensors are located. Once starting the training program, the subject will receive instructions appearing in the graphic VR environment:

Neck movements

The software will guide the subjects to perform neck movements.

EVALUATIONS

Physiotherapist Evaluation and Assessment of Videos

1. Identification of each movement seen in the video from the list detailed in "Neck Movement" section
2. Determining if the use of such movement is recommended for rehabilitation

Safety

All adverse events (AEs) will be documented and evaluated as part of the risk management for the device

	Study Protocol			
	VRP-CLINIC SOFTWARE EVALUATION - IN SUPPORT OF REHABILITATION			
Protocol#	VRP02	Version #, Date.	Version 01 22-March-2017	Page 10 of 12

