STATISTICAL CONSIDERATIONS AND ANALYSIS

Sample Size Justification

The rationale for the sample size is based on obtaining exact 95% confidence intervals for the activity movements which achieved 80% success. When the sample size is 20, a one-sided 95.0% confidence interval for a single proportion using the large sample normal approximation will extend at most 0.18 from the observed proportion.

Subject Accountability

A CONSORT flow diagram will be presented that will include the number of subjects screened and reasons for screening failures; the number of subjects, who were enrolled, as well as the reasons for all enrollment discontinuations grouped by major reason; A list of discontinued subjects, protocol deviations, and subjects excluded from the analyses.

Data Analysis

Descriptive statistics and summary tables will be provided giving sample size, absolute and relative frequency of categorical variables and sample size, arithmetic mean, standard deviation, median, minimum and maximum, percentiles and 95% CI (Confidence Interval) for means of continuous variables. All measured variables and derived parameters will be listed individually and, if appropriate, tabulated by descriptive statistics.

Study Hypothesis – Primary Endpoint:

The number and percentage of neck movements which achieve a success rate of at least 80% will be tabulated. Exact 95% binomial confidence intervals will be calculated for the rate of neck movements which achieve 80% success.

Safety - Secondary Endpoint

Adverse events will be coded according to coding dictionaries (MedDRA version 13.1 or higher) and presented in tables by system organ class, preferred term. The number and percentage of subjects who experienced any adverse events will be tabulated.

ADVERSE EVENTS

In this study, Serious Adverse Experience (SAE) is to be reported by the investigator within 24h to the IRB. The “Adverse Experience” CRF should be filled in all events of SAE and in other cases of Adverse Experience (AE) which, in the judgment of the investigator, affect this protocol.

Anticipated Side Effects

In this study, we are not anticipating any side effects.

Anticipated Adverse Effects/Risks

The movements not expected to cause any pain or discomfort.

	Study Protocol			
	VRP-CLINIC SOFTWARE EVALUATION - IN SUPPORT OF REHABILITATION			
Protocol#	VRP02	Version #, Date.	Version 01 22-March-2017	Page 11 of 12

MISCELLANEOUS

Ethical Considerations

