Prior to study initiation the site shall obtain an Institutional Review Board (IRB)/Helsinki approval of the study. Any changes in the study protocol, informed consent forms, or investigator must be re-approved by the IRB and the approval documented. All subjects enrolled in the study will provide their consent prior to entering the study. An informed consent form shall be signed by the subject. The investigator will retain the forms as part of the study records.

This study will be performed in accordance with the Declaration of Helsinki, in agreement with the guidelines for conducting a clinical investigation in accordance with the principles of ICH GCP outlined in the E6 document and IRB guidelines. By signing the present protocol, participants in the study commit themselves to carry it out in accordance with local legal requirements

Protocol Amendments

Possible with IRB approval.

Study Monitoring

Study monitoring visits include a pre-study site evaluation and site initiation visit, periodic monitoring visits during the course of the investigation, and a final termination visit at the conclusion of the study. The frequency of the monitoring visits will vary depending on the subject enrollment rate, the quantity and quality of data collection.

Study Documentation

Study documents include protocol and MOH documents, approvals, insurance, signed ICFs, copy of CRFs, training materials, SAE reports, investigator site file

Case Report Forms (CRFs)

Case Report Forms will be established to collect the required demographic and clinical information, as described by this protocol and the variables to be analyzed. Case Report Forms will be completed by the investigator or a designee who will be properly trained on study procedures and data recording requirements. The investigator will maintain a separate enrollment log with the corresponding subject name, initials and subject code. All CRFs will have 1 original clearly filled with a ball point pen. Any changes, amendments or additions to the forms will have to be marked though with a single line, dated, and initialed. The investigators will maintain a copy of the CRFs.

Study Termination

If the Principal Investigator determines that the conditions do not allow the continuation of the study, then it will be terminated. Among the conditions that may justify the study termination without limitation are the followings:

- Subject safety
- Inability to enroll subjects at acceptable rate

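### The adverse event form is required for only some non-serious events, yet the protocol promises to record and tabulate all of them

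*Combined protocol and SAP*

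**What the plan says.** Four places ask for all AEs, with no condition on seriousness or consequence:

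- Synopsis, Study Endpoints: "All AEs will be recorded and evaluated as part of the risk management for the device".
- Study Design, Overview: "The study team will record any adverse event (AE) if such happens during/post training".
- Endpoints, Secondary Endpoint: "Record of any adverse event occurring during the study".
- Evaluations, Safety: "All adverse events (AEs) will be documented and evaluated as part of the risk management for the device".

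The analysis matches them. Under Safety - Secondary Endpoint in the statistical section: "The number and percentage of subjects who experienced any adverse events will be tabulated".

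The Adverse Events section sets a different rule for the form. The AE CRF is to be completed for every serious event and for "other cases of Adverse Experience (AE) which, in the judgment of the investigator, affect this protocol". The documents do not say what it means for an event to affect the protocol.

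The Case Report Forms section says the CRFs are set up "to collect the required demographic and clinical information, as described by this protocol and the variables to be analyzed". The list under Study Documentation includes CRF copies and SAE reports but no AE log.

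**The concern.** The endpoint and its table cover all AEs, but the rule for completing the AE form covers only a subset. The subset is set by a judgment for which no criterion is given. A non-serious event judged not to affect the protocol counts towards the endpoint, yet nothing in the Adverse Events section requires it to reach the form from which one would expect the table to be built.

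The events most exposed are the minor, transient ones. They are also the kind most likely in a session of about 5 minutes in healthy adults, under a protocol that states that it expects no side effects. Safety is the only labelled secondary endpoint, and all AEs are meant to feed the device's risk management. A reader shown a table with no AEs could not tell whether none occurred or none passed the filter.

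**Working it through.** The plan states no figure on this point, so there is none to reproduce. The check has two parts: a comparison of the rules, and an illustration of size.

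**1. The rules side by side**

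| Place | Serious AE | Non-serious AE judged to affect the protocol | Other non-serious AE |
|---|---|---|---|
| Synopsis; Overview; Endpoints; Evaluations | recorded | recorded | recorded |
| Safety analysis table | counted | counted | counted |
| AE form rule (Adverse Events section) | form required | form required | form not required |

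The rules part company only in the last column. For those events the protocol asks for a record and a count, but its form rule does not ask for the form, and no other collection route is described.

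**2. Size**

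From the documents: n = 20 subjects. One subject is 1/20 = 5 percentage points.

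Assumed, because the documents give no AE rate:
- p, the true proportion of subjects with an AE: 5% to 30%.
- c, the share of those subjects with an event that passes the filter: 1, 0.5 or 0.25.
- Subjects are independent.

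Expected number of subjects tabulated = 20 × p × c. At p = 0.20 this is 20 × 0.20 × 1 = 4, 20 × 0.20 × 0.5 = 2, and 20 × 0.20 × 0.25 = 1.

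Chance that the table shows no AE = (1 − p × c)^20. For example, at p = 0.10 and c = 0.5 it is (1 − 0.05)^20 = 0.95^20 = 0.3585.

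| True rate p | c = 1 (no loss) | c = 0.5 | c = 0.25 |
|---|---|---|---|
| 5% | 35.8% | 60.3% | 77.8% |
| 10% | 12.2% | 35.8% | 60.3% |
| 20% | 1.2% | 12.2% | 35.8% |
| 30% | 0.1% | 3.9% | 21.0% |

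The effect on one result can be shown with exact two-sided 95% intervals. If 2 of 20 subjects have an AE, the rate is 10% (1.2% to 31.7%). If both are left off the form, the report reads 0 of 20 (0% to 16.8%).

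**The case against.** The best case for the plan is that nothing is strictly contradicted. The four all-AE statements say what must be recorded, and the later sentence says only when one named form must be filled in. It does not forbid recording other events elsewhere, so a study team could obey every statement at once. Because recording any AE is itself the secondary endpoint, one could also argue that every AE affects the protocol. The CRF section says that CRFs collect the variables to be analysed, and any AE is such a variable. The CRFs themselves are not in the documents and may have a suitable field. Exposure is small: one centre, one visit, 30 minutes per subject.

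Part of this stands. Omission is possible, not certain, and a broad reading removes the problem. The rates and pass shares above are illustrations, and the protocol attaches no decision or threshold to the AE rate. Withdrawn subjects may be replaced, so the denominator could exceed 20 and the 5-point step would then be slightly smaller.

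It does not rescue the wording. If every AE affected the protocol, the condition on non-serious events would do no work, so the sentence invites a narrower reading. If non-serious events sit only in source notes, the table still has no defined data source. The CRF section's general statement supports capturing all AEs, but that sets it against the specific form rule and does not settle which one governs.

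**Conclusion.** The concern holds. The form rule is narrower than the endpoint and the table it should supply, and an investigator who follows it as written can leave non-serious AEs out of the safety data. Any resulting bias in the percentage of subjects with an AE is downward, by 5 points per omitted subject with 20 analysed. How often this would happen cannot be known from the documents. It depends on the true AE rate and on how an undefined condition is read, and it is nil under the broadest reading.

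The importance is moderate, and the wording should be fixed. The endpoint is secondary and descriptive, only non-serious events are at risk, and neither the capture of serious events nor the primary endpoint is touched. The mismatch between the texts is certain. Actual under-reporting is only a possibility.

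**What to change.** Replace the sentence on the form in the Adverse Events section with:

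> The Adverse Experience CRF will be completed for every AE, serious or not, regardless of relation to the device or effect on the protocol.

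Leave the 24-hour rule for reporting serious events as it is. The form, the endpoint and the table then cover the same events.

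The cost is one sentence, a few short form entries for 20 subjects seen once, and ethics review, since "Any changes in the study protocol, informed consent forms, or investigator must be re-approved by the IRB". The change should be in place before the first subject is enrolled, because a minor event not written down at a single visit may not be recoverable later.
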